
Events of gastrointestinal perforation have been reported in clinical trials although the role of Janus-kinase inhibition in these events is not known.
 
XELJANZ should be used with caution in patients who may be at increased risk for gastrointestinal perforation (e.g., patients with a history of diverticulitis and patients with concomitant use of corticosteroids and/or nonsteroidal anti-inflammatory medicinal products). Patients presenting with new onset abdominal signs and symptoms should be evaluated promptly for early identification of gastrointestinal perforation.
			
Question No.	Question	Desired Response	Question Category
Q7. Please select the best response (True, False, I don't know) for each of the following statements about risks and use of tofacitinib. .			
Q7e	Tofacitinib should be used with caution in patients who may be at increased risk for gastrointestinal perforation.	True	Knowledge of Key Risk Message

090177e199ebc283\Approved\Approved On: 11-Apr-2022 22:32 (GMT)

Key Risk Message 8: Venous thromboembolism (VTE) risk			

Serious VTE events including pulmonary embolism (PE), some of which were fatal, and deep vein thrombosis (DVT) have been observed in patients taking tofacitinib. A dose dependent increased risk for VTE was observed in clinical study with tofacitinib, compared to Tumour Necrosis Factor (TNF) inhibitors.
			

 1. Prior to initiation of treatment, prescribers should assess patients for risk factors of VTE. Tofacitinib should be used with caution in patients with known risk factors for VTE, regardless of indication and dosage. 2. Prescribers should discuss the signs and symptoms of VTE with their patients. 3. Prescribers should promptly evaluate patients with signs and symptoms of VTE and discontinue tofacitinib in patients with suspected VTE, regardless of dose or indication. 4. Tofacitinib 10 mg film-coated tablets twice daily for maintenance treatment is not recommended in patients with UC who have known venous thromboembolism (VTE) risk factors, unless there is no suitable alternative treatment available. 5. For patients with UC who are not at increased risk for VTE, tofacitinib 10 mg orally twice daily may be considered if the patient experiences a decrease in response on tofacitinib 5 mg twice daily and failed to respond to alternative treatment options for ulcerative colitis such as TNF inhibitor treatment. Tofacitinib 10 mg twice daily for maintenance treatment should be used for the shortest duration possible. The lowest effective dose needed to maintain response should be used. 			
Question No.	Question	Desired Response	Question Category
Q8. In your clinical practice, before starting a patient on tofacitinib, which of the following do you check or ask?			
Q8e	Is this patient at an increased risk for venous thromboembolism (VTE)?	(selected Yes)	Adherence to Key Risk Messages
Q7. Please select the best response (True, False, I don't know) for each of the following statements about risks and use of tofacitinib.			
Q7h	Assuming there are other treatment options, tofacitinib 10 mg twice daily can be used in patients with venous thromboembolism (VTE) risk factors.	False	Knowledge of Key Risk Message

090177e199ebc283\Approved\Approved On: 11-Apr-2022 22:32 (GMT)

Q10. In your clinical practice, which actions would you take when faced with the following scenarios during tofacitinib **treatment maintenance**? **Assume in all scenarios that the patient is receiving tofacitinib 5 mg twice daily unless otherwise noted.** Select the best response for each scenario: “I would discontinue tofacitinib,” “I would interrupt dosing,” “I would lower the dose,” OR “I would take no action.”

Q10h	The patient has a suspected venous thromboembolism (VTE).	“I would discontinue tofacitinib”	Knowledge of Key Risk Message
------	---	-----------------------------------	-------------------------------

Key Risk Message 9: Patient counseling

It is important for prescribers to discuss the risks associated with use of XELJANZ with their patients, and in applicable instances, with their caregivers.

It is important for physicians to:

- 1. Provide the patient alert card to each patient who is prescribed with XELJANZ;**
- 2. Remind patients to use the patient alert card;**
3. Discuss the risks with each patient and ensure patient understanding of the treatment potential risks; and
- 4. Ensure patients carry the patient alert card with them, particularly when they visit a doctor’s office and/or the emergency room.**

Question No.	Question	Desired Response	Question Category
--------------	----------	------------------	-------------------

[QUESTION APPLIES TO ALL COUNTRIES]

Q11. In your clinical practice, how frequently do you perform each of these activities when **initiating treatment** with tofacitinib? Please select the best response: “Always,” “Sometimes,” or “Never.”

Q11a	Give the tofacitinib patient alert card to the patient.	“Always” or “Sometimes”	Adherence to Key Risk Message
------	---	-------------------------	-------------------------------

Q11b	Advise the patient to inform you immediately if they experience any of the symptoms on the tofacitinib patient alert card.	“Always” or “Sometimes”	Adherence to Key Risk Message
------	--	-------------------------	-------------------------------

090177e199ebc283\Approved\Approved On: 11-Apr-2022 22:32 (GMT)

Q11c	Advise patients to carry the tofacitinib patient alert card with them, particularly when they visit a doctor, a hospital, or Accident and Emergency.	“Always” or “Sometimes”	Adherence to Key Risk Message
Q11d	Discuss the signs and symptoms of venous thromboembolism (VTE) with the patient.	“Always” or “Sometimes”	Adherence to Key Risk Message

[QUESTION APPLIES TO ALL COUNTRIES]			
Wrong Answer Options Not Associated with a Key Risk Message			
Q8. In your clinical practice, before starting a patient on tofacitinib, which of the following do you check or ask?			
Q8a	Does this patient have gastroesophageal reflux disease (GORD)?	No	Adherence to Key Risk Messages
Q8d	Does this patient have a history of hyperthyroidism?	No	Adherence to Key Risk Messages

Other questions:

[QUESTION APPLIES TO ALL COUNTRIES]			
Consent Question			
Question No.	Question	Desired Response	Question Category
N/A	Do you agree to proceed with this survey?	Yes	Consent

This question is contained in the invitation and consent form.

[QUESTIONS APPLY TO ALL COUNTRIES]			
Screening Questions			
Question No.	Question	Desired Response	Question Category
S1.	Are you currently employed by Pfizer?	No	Screening
S2.	Within the past 12 months, have you prescribed tofacitinib for ulcerative colitis? Please consider both new and repeat prescriptions.	Yes	Screening

[QUESTIONS APPLY TO ALL COUNTRIES]			
HCP Practice Characteristics			
Question No.	Question	Desired Response	Question Category
D1.	What is your main medical specialty? Select one.	N/A	HCP Practice Characteristics
D2.	After completing all specialist training, for how many years have you been in practice? Please select one.	N/A	HCP Practice Characteristics
Q1.	When was the last time you prescribed tofacitinib? Please consider both new and repeat prescriptions. Please select one response.	N/A	HCP Practice Characteristics

090177e199ebc283\Approved\Approved On: 11-Apr-2022 22:32 (GMT)

[QUESTIONS APPLY TO ALL COUNTRIES]			
HCP Practice Characteristics			
Q2.	Within the last 12 months, how many prescriptions for tofacitinib have you written for ulcerative colitis? Please think of the total number of prescriptions – both new and repeat – and not the number of patients. Please select one.	N/A	HCP Practice Characteristics
Q3.	Within the last 12 months, how many patients have you treated with tofacitinib for ulcerative colitis? Please select one.	N/A	HCP Practice Characteristics
Q4.	Which of the following statements best describes your involvement in tofacitinib treatment for most of your patients? Please select one.	N/A	HCP Practice Characteristics
Q5.	Have you ever participated in a Pfizer-sponsored tofacitinib clinical trial as a healthcare provider? Please select one response.	N/A	HCP Practice Characteristics

090177e199ebc283\Approved\Approved On: 11-Apr-2022 22:32 (GMT)

Awareness (Receipt), Utilisation of and Attitude towards the Xeljanz aRMM Materials				
Question No.	Question	Desired Response	Question Category	Applicable Survey Countries
				All countries
Q13.1a.	Have you ever received a prescriber brochure for tofacitinib ? Please select one.	Yes	Awareness (Receipt)	
Q13.1b.	The prescriber brochure for tofacitinib was updated in 2020. Did you receive a prescriber brochure after February 2020 [January 2020 for Poland]? Please select one.	Yes	Awareness (Receipt)	
Q13.2	Have you read the prescriber brochure for tofacitinib ? Select one.	“Yes, all of it” OR “Yes, some of it”	Utilisation	

090177e199ebc283\Approved\Approved On: 11-Apr-2022 22:32 (GMT)

Q13.3	How useful or not useful do you find the prescriber brochure for tofacitinib in your clinical practice?	“Very useful” or “Somewhat useful”	Attitude towards the aRMM Materials	
				All Countries Except Germany
Q14.1.a	Have you ever received the prescriber treatment initiation checklist for tofacitinib ? Please select one.	Yes	Awareness (Receipt)	
Q14.1b.	Did you receive the prescriber treatment initiation checklist for tofacitinib after February 2020 [January 2020 for Poland]? Please select one.	Yes	Awareness (Receipt)	

Q.14.2	How often do you use the prescriber treatment initiation checklist for tofacitinib when writing a new prescription of tofacitinib for a patient? Please select one.	“All of the time”, “Most of the time” or “Some of the time”	Utilization	
Q14.3	How useful or not useful do you find the prescriber treatment initiation checklist for tofacitinib in your clinical practice? Please select one.	”Very useful” or “Somewhat useful”	Attitude towards the aRMM Materials	
Q15.1.a	Have you ever received the prescriber treatment maintenance checklist for tofacitinib ? Please select one.	Yes	Awareness (Receipt)	All countries, except Germany

090177e199ebc283\Approved\Approved On: 11-Apr-2022 22:32 (GMT)

Q15.1.b.	Did you receive the prescriber treatment maintenance checklist for tofacitinib after February 2020 [January 2020 for Poland]? Please select one.	Yes	Awareness (Receipt)	All countries, except Germany
Q15.2	How often do you use the prescriber treatment maintenance checklist for tofacitinib when writing a maintenance prescription of tofacitinib for a patient? Please select one.	“All of the time”, “Most of the time” or “Some of the time”.	Utilization	
Q15.3	How useful or not useful do you find the prescriber treatment maintenance checklist for tofacitinib in your clinical practice? Please select one.	“Very useful” or “Somewhat useful”	Attitude towards the aRMM Materials	

090177e199ebc283\Approved\Approved On: 11-Apr-2022 22:32 (GMT)

Q14.1.i.a	Have you ever received the prescriber treatment checklist for tofacitinib ? Please select one.	Yes	Awareness (Receipt)	Germany only
Q14.1.i.b	Did you receive the prescriber treatment checklist for tofacitinib after February 2020? Please select one.	Yes	Awareness (Receipt)	
Q14.2.i.	How often do you use the prescriber treatment checklist for tofacitinib when writing a new prescription of tofacitinib for a patient? Please select one.	“All of the time”, “Most of the time” or “Some of the time”	Utilization	
Q14.3.i.	How often do you use the prescriber treatment checklist for tofacitinib when writing a maintenance prescription of tofacitinib for a patient? Please select one.	“All of the time”, “Most of the time” or “Some of the time”	Utilization	

090177e199ebc283\Approved\Approved On: 11-Apr-2022 22:32 (GMT)

Q14.4.i.	How useful or not useful do you find the prescriber treatment checklist for tofacitinib in your clinical practice? Please select one.	“Very useful” or “Somewhat useful”	Attitude towards the aRMM Materials	
Q16.1a.	Have you ever received a supply of tofacitinib patient alert cards ? This is a card which is designed to be given to patients. Please select one.	Yes	Awareness (Receipt)	All Countries
Q16.1b	Did you receive a supply of tofacitinib patient alert cards after February 2020 [January 2020 for Poland]? Please select one.	Yes	Awareness (Receipt)	
Q16.2	How useful or not useful did you find the tofacitinib patient alert card in your clinical practice?	“Very useful” or “Somewhat useful”	Attitude towards the aRMM Materials	

A17.1	Are you aware of a prescriber website for tofacitinib where you can obtain prescribing information and where you can view and/or download the tofacitinib prescriber brochure, prescriber treatment checklists, and patient alert card? Please select one.	Yes	Awareness	
Q17.2	Have you ever visited the prescriber website for tofacitinib ? Please select one	Yes	Utilization	
A17.3	How useful or not useful do you find the prescriber website for tofacitinib in your clinical practice? Please select one.	“Very useful” or “Somewhat useful”	Attitude towards the aRMM Materials	

090177e199ebc283\Approved\Approved On: 11-Apr-2022 22:32 (GMT)

[QUESTION APPLIES TO ALL COUNTRIES]			
Source of HCPs' Information on the Safety of Xeljanz			
Question No.	Question	Desired Response	Question Category
Q12	Which of the following is your primary source of safety and prescribing information for tofacitinib? Please select one	N/A	Source of HCPs' Information on the Safety of Xeljanz

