In July 2018, Xeljanz 5-mg tablet and 10-mg tablet (immediate-release) was approved by the EC for the treatment of moderately-to-severely active ulcerative colitis (UC) in patients with an inadequate response, a loss of response, or an intolerance to conventional therapy or a biologic agent. UC is a bowel disease characterized by inflammation and ulcers in the colon and rectum. In clinical trials, patients treated with 5 or 10 mg of Xeljanz BID were more likely to achieve and maintain a clinical response and remission of their condition as compared to patients in the placebo group.⁴ The approved doses of Xeljanz for the treatment of moderately-to-severely active UC are 10 mg BID for induction and 5 mg BID for maintenance. Some patients (patients who have failed to respond to alternative treatment options for UC such as tumour necrosis factor inhibitor [TNF inhibitor] treatment) who have a reduction in response to 5 mg BID maintenance treatment may benefit from an increase in maintenance dose to 10 mg BID; for these patients, the presence of known risk factors for venous thromboembolism (VTE) should be considered. Xeljanz 10 mg BID for maintenance treatment should be used for the shortest duration possible.⁵

To provide an appropriate tool designed to enhance the awareness and knowledge of HCPs and patients about important safety concerns (including: serious and other important infections, herpes zoster reactivation, decrease in neutrophil counts and neutropenia, decrease

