In May 2019, the EC requested a reassessment of the benefit-risk of Xeljanz pursuant to Article 20 of Regulation (EC) No 726/2004 due to a signal for increased risks of pulmonary embolism and mortality arising in an ongoing MAH-sponsored Phase 3b/4 safety study (A3921133) designed to evaluate the risk of malignancy and major adverse cardiac events in RA patients aged 50 years and older who had at least one cardiovascular risk factor. In November 2019, the Committee on Human Medicinal Products (CHMP) concluded, based on a recommendation from the Pharmacovigilance Risk Assessment Committee (PRAC), that patients treated with Xeljanz are at increased risk of VTE events, both for deep venous thrombosis as well as pulmonary embolism, especially in patients with risk factors for VTE. The PRAC further concluded that the risk of VTE events is dose-dependent. To minimise this risk, the PRAC recommended that warnings be added to the Summary of Product Characteristics (SmPC) regarding the increased risk of VTE observed in patients taking Xeljanz, especially for patients with known risk factors for VTE. The PRAC also recommended that treatment with Xeljanz be discontinued in patients with suspected VTE and that Xeljanz 10 mg BID for maintenance treatment is not recommended in patients with UC who have known VTE risk factors, unless there is no suitable alternative treatment available. Clarifications on the posology were also added particularly for UC patients in maintenance. PRAC also concluded that, based on the interim analyses of Study A3921133, there is a potential increased risk of mortality. This was partly driven by an increased risk of serious infections among patients aged 65 years and above. As such, Xeljanz should be considered among patients over 65 years of age only if no suitable alternative treatment is available. These conclusions and revisions to the SmPC, were approved by the EC on 31 January 2020.⁵

The aRMM materials were updated to reflect the findings from the CHMP's re-assessment of the benefit-risk of Xeljanz (hereafter referred to as the "current aRMM materials"); the projected current aRMM materials distribution date for each survey country can be found in Table 1.

Based on the content of the Xeljanz Prescriber Brochure and prescriber treatment checklists, the following key risk messages will be assessed:

- Key risk message 1: Use in special populations;

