Q2. Within the last 12 months, how many **prescriptions** for tofacitinib have you written for ulcerative colitis? Please think of **the total number of prescriptions** – both new and repeat – and not the number of patients. Please select one.

a	Fewer than 10 prescriptions	
b	10 to 20 prescriptions	
c	21 to 50 prescriptions	
d	More than 50 prescriptions	

Data: Single punch.

090177e199ebc283\Approved\Approved On: 11-Apr-2022 22:32 (GMT)

[QUESTION APPLIES TO ALL COUNTRIES]

Q3. Within the last 12 months, how many **patients** have you treated with tofacitinib for ulcerative colitis? Please select one.

a	Fewer than 5 patients	
b	5 to 10 patients	
c	11 to 20 patients	
d	More than 20 patients	

Data: Single punch.

[QUESTION APPLIES TO ALL COUNTRIES]

Q4. Which of the following statements best describes your involvement in tofacitinib treatment for most of your patients? Please select one.

a	I'm involved only in the initiation of tofacitinib treatment. I refer patients to another practice for follow up and monitoring.	
b	I'm involved in both the initiation and maintenance of tofacitinib treatment.	
c	I'm involved only in the maintenance and monitoring of patients who were prescribed tofacitinib by another HCP.	

Data: Single punch.

[QUESTION APPLIES TO ALL COUNTRIES]

Q5. Have you ever participated in a Pfizer-sponsored tofacitinib clinical trial as a healthcare provider? Please select one response.

a	Yes	
b	No	
c	I'm not sure	

Data: Single punch.

[QUESTIONS ABOUT KNOWLEDGE OF KEY RISK MESSAGES FOR TOFACITINIB]

[QUESTION APPLIES TO ALL COUNTRIES]

Next, the third section of questions are designed to assess your understanding of the contraindications and risks of tofacitinib.

Q6. Please select the best response (True, False, I don't know) for each of the following statements about contraindications of tofacitinib.

		True	False	I don't know
a	Tofacitinib may be administered to patients with severe hepatic impairment.			
b	Tofacitinib is contraindicated in patients who are pregnant or lactating.			

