c	Tofacitinib is contraindicated in patients with moderate renal impairment.			
d	Tofacitinib is contraindicated in patients with active tuberculosis (TB) or other severe infections such as sepsis or opportunistic infections.			

Data: Single punch per row.

Data: Answer options will be displayed in a random order for each survey participant.

Answer: Points a and c are wrong answers.

[QUESTIONS ABOUT KNOWLEDGE OF KEY RISK MESSAGES FOR TOFACITINIB]

[QUESTION APPLIES TO ALL COUNTRIES]

Q7. Please select the best response (True, False, I don't know) for each of the following statements about risks and use of tofacitinib.

		True	False	I don't know
a	Tofacitinib can be used in combination with biologic drugs or potent immunosuppressants, such as azathioprine, cyclosporine, 6-mercaptopurine, or tacrolimus.			
b	The possibility exists for tofacitinib to affect host defenses against malignancies.			
c	Live vaccines should not be given concurrently with tofacitinib.			
d	Prior to administering tofacitinib, it is NOT necessary to check patients' laboratory parameters including lymphocytes, neutrophils, and haemoglobin.			
e	Tofacitinib should be used with caution in patients who may be at increased risk for gastrointestinal perforation.			
f	When taking tofacitinib, the risk of herpes zoster is increased when the lymphocyte count (ALC) is lower than 1.0 cells x 10 ⁹ /L.			
g	Tofacitinib should only be considered in patients who are 65 years of age or older if there is no suitable alternative.			
h	Assuming there are other treatment options, tofacitinib 10 mg twice daily can be used in patients with venous thromboembolism (VTE) risk factors.			

Data: Single punch per row.

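### UC knowledge item Q7h drops the maintenance limit of its source message, so a respondent thinking of induction can support an answer that is scored wrong

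*Protocol*

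**What the plan says.** In the UC questionnaire (Protocol, Appendix 2), Q7 asks for the best response of True, False or I don't know "for each of the following statements about risks and use of tofacitinib". Item h reads "Assuming there are other treatment options, tofacitinib 10 mg twice daily can be used in patients with venous thromboembolism (VTE) risk factors". The answer note marks a, d and h as wrong statements, so only False scores. Appendix 4 repeats the item in the same words and maps it to Key Risk Message 8.

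The messages behind it in Appendix 4 (Key Risk Message 8, UC) are:

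- Message 4, which makes an exception where no suitable alternative exists: "Tofacitinib 10 mg film-coated tablets twice daily for maintenance treatment is not recommended in patients with UC who have known venous thromboembolism (VTE) risk factors".
- Message 5, on patients not at increased VTE risk, also concerns maintenance: "Tofacitinib 10 mg twice daily for maintenance treatment should be used for the shortest duration possible".
- Message 1, which names no phase: "Tofacitinib should be used with caution in patients with known risk factors for VTE, regardless of indication and dosage".

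Section 6 reports the PRAC recommendation with the same limit as message 4: "Xeljanz 10 mg BID for maintenance treatment is not recommended in patients with UC who have known VTE risk factors". It also states the dosing: "The approved doses of Xeljanz for the treatment of moderately-to-severely active UC are 10 mg BID for induction and 5 mg BID for maintenance".

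Section 8.7.3 lists the proportion correct on each of the 20 UC knowledge questions under primary analysis. Section 8.3 sets the UC knowledge criterion: at least 80% of HCPs with at least 16 of 20 correct.

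**The concern.** Q7h tests a broader statement than the message it is meant to test. Message 4 concerns 10 mg twice daily in maintenance. Q7h concerns 10 mg twice daily in general, and in UC that dose is also the standard induction dose. A respondent who has induction in mind can find support in the protocol's own text for answering True, and is then recorded as not knowing the VTE message.

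The survey admits respondents for whom induction may come to mind first: Q4 of the UC questionnaire offers the role "involved only in the initiation of tofacitinib treatment". Nothing earlier in the questionnaire supplies the limit. The other UC items on 10 mg twice daily (Q10c and Q10e) sit under a stem that says treatment maintenance, but Q10 comes after Q7, and section 8.6.4 does not let respondents go back.

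At stake is how one item is interpreted. Table 4 counts two UC knowledge items on VTE, and Q7h is one of them. VTE is also the risk that prompted the update of the materials (section 6). A low Q7h result could be reported as failed communication when part of it is item wording.

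**Working it through.** **Wording, side by side**

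| Source | Dose | Phase | Position with VTE risk factors |
|---|---|---|---|
| Key Risk Message 8, message 4 (Appendix 4) | 10 mg twice daily | maintenance | not recommended unless no suitable alternative |
| PRAC recommendation (section 6) | 10 mg twice daily | maintenance | not recommended unless no suitable alternative |
| Key Risk Message 8, message 1 (Appendix 4) | any | none named | use with caution |
| Approved dosing (section 6) | 10 mg twice daily | induction | approved dose; VTE risk factors not addressed in that sentence |
| Q7h (Appendices 2 and 4) | 10 mg twice daily | none named | keyed as not usable if alternatives exist |

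The first two rows give False. Rows three and four together give a respondent thinking of induction a basis for True.

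**Inputs for the size**

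- From the protocol: 20 items, pass mark 16, target share 80% (section 8.3); 300 completed surveys (section 8.5).
- Assumed: q, the probability of a correct answer on each item without misreading, and r, the share of otherwise-correct respondents who answer True because they read Q7h as covering induction. Neither is in the documents, so both are shown over a range. Items are taken as independent.

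**The plan's own precision figure.** 1.96 × √(0.5 × 0.5 / 300) = 0.0566, which matches the stated 5.7%.

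**Effect on the item.** The proportion correct becomes q(1 − r). At q = 0.85:

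- r = 5%: 0.85 × 0.95 = 80.8%
- r = 10%: 0.85 × 0.90 = 76.5%
- r = 20%: 0.85 × 0.80 = 68.0%

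For scale, the 95% half-width at 85% with 300 surveys is 1.96 × √(0.85 × 0.15 / 300) = 4.0 points.

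**Effect on the 16-of-20 criterion.** Losing Q7h changes a respondent's result only if exactly 15 of the other 19 items are correct. So

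share passing = P(Bin(20, q) ≥ 16) − r × q × P(Bin(19, q) = 15).

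| q | No misreading | P(Bin(19, q) = 15) | r = 10% | r = 20% | Drop at r = 20% | r at which the share falls to 80% |
|---|---|---|---|---|---|---|
| 0.84 | 79.4% | 0.1858 | 77.8% | 76.3% | 3.1 points | already below |
| 0.845 | 81.2% | 0.1789 | 79.7% | 78.2% | 3.0 points | about 8% |
| 0.85 | 83.0% | 0.1714 | 81.5% | 80.07% | 2.9 points | about 20.5% |
| 0.86 | 86.3% | 0.1550 | 84.9% | 83.6% | 2.7 points | about 47% |
| 0.90 | 95.7% | 0.0798 | 95.0% | 94.2% | 1.4 points | never |

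Worked line, q = 0.85 and r = 20%: 0.8298 − 0.20 × 0.85 × 0.1714 = 0.8298 − 0.0291 = 0.8007.

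If items are correlated (beta-binomial, intraclass correlation 0.05 to 0.20), the drop at r = 20% is 0.8 to 2.2 points over q from 0.84 to 0.90. The half-width for a share of 80% with 300 surveys is 1.96 × √(0.8 × 0.2 / 300) = 4.5 points.

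**The case against.** The strongest reply is that the item works as written. The stem asks for the best response. An unqualified claim that the dose can be used has to hold in every phase to be true, and it fails in maintenance. The opening condition about other treatment options echoes the exception in message 4 and points the reader there. Within Key Risk Message 8, the messages that name 10 mg twice daily alongside VTE risk both point to False. Section 6 does not say what to do at induction for a patient with VTE risk factors and alternatives, so the case for True is indirect. The amendment log records completed user testing of the English questionnaire with edits to Q7, section 8.8.1.1 plans further testing in each country, and nothing in the protocol shows that anyone misread the item. VTE is also covered by Q10h, Q8e and Q11d.

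Most of this stands. It establishes that False is the right key, that r is unknown and that Q7h should not be read alone. It does not supply the missing limit: the version 3.0 wording still lacks it after that testing, and the phase-free caution in message 1 permits use.

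A reader might infer that the key is wrong or that the UC knowledge conclusion is unreliable. The documents support neither. A reader might equally infer that the 80% conclusion is never affected. That is too strong as well, since at q = 0.845 an r of about 8% is enough to cross.

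**Conclusion.** The point holds as an ambiguity in one of 20 UC knowledge items. The likely consequence is a downward bias in the Q7h per-item result, of a size that cannot be derived from the documents. On the assumed values it could exceed the item's own sampling error: at q = 0.85, a drop of 8.5 points at r = 10% against a half-width of 4.0.

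For the 16-of-20 criterion the effect is small, about 3 points at most at r = 20% for q between 0.84 and 0.90 with independent items, and less with correlated items. It changes the 80% conclusion only when the share is already close to 80%. No success threshold rests on Q7h alone. Severity is at the low end of minor, and the remedy is a cheap improvement.

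**What to change.** For this study, keep the primary scoring. Report the True / False / I don't know split for Q7h, overall and by Q4 role, with a footnote that the item omits the maintenance limit, so that a low result is not read solely as failed communication of the VTE message. Rewording cannot help now: by Table 1 the planned windows had closed in seven of the eight countries before version 3.0 was dated, and changing the item for Romania alone would break comparability.

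Do not add an analysis that credits True on Q7h. It would also credit respondents who do not know the restriction. At q = 0.84 the share passing is 79.4%, but crediting every True could raise it to P(Bin(19, 0.84) ≥ 15) = 82.4%, turning a fail into a pass.

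For any later use, insert *for maintenance treatment* after *twice daily* in Q7h in Appendix 2, Appendix 4 and the translations.

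The cost is one small table and a footnote now, and three words plus translations later. A reworded item would not be directly comparable with this survey's Q7h result.
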